- **Airway swelling or edema.** A described complication of the LT is the development of major tongue, pharyngeal or hypopharyngeal swelling, which may interfere with ventilation. While usually associated with instances of prolonged LT ventilation (several hours), some clinicians have reported the occurrence of this event during resuscitative efforts. This event

will be based upon EMS and ED personnel assessment and will be determined from EMS and ED patient care records. The timeframe for surveillance for this event will be limited to the earlier of a) replacement of the LT with an ET tube, or b) the first 24 hours of hospitalization. While generally associated with LT insertion, we will monitor the occurrence of airway swelling or edema regardless of inserted airway device.

- **Oropharyngeal or hypopharyngeal injury.** Advanced airway insertion may result in injury to the oropharynx and hypopharynx, including soft tissue lacerations, injury to teeth, and perforation of pharyngeal, hypopharyngeal or other anatomic structures, among others. This event will be determined by review of the discharge summary and ED physician records and will be limited to injuries identified during the first 24 hours of hospitalization.
- **Pneumothorax.** Airway insertion and ventilatory efforts may cause pulmonary barotrauma, resulting in pneumothorax. This event will be determined from radiology or ED physician interpretation of the first chest x-ray or computed tomography (CT) performed in the ED.
- **Pneumonia and aspiration pneumonitis.** Pneumonia and aspiration pneumonitis are known sequelae of cardiac arrest and airway management. This event will be defined as the presence of an infiltrate or consolidation as reported by radiology interpretation of chest x-rays or computed tomography (CT) performed during the first 72 hours of hospitalization.

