#### **19.1.2 Hospital Data**

Hospital records that will be reviewed for this trial may include:

- Emergency Department and inpatient physician clinical documentation
- Emergency Department and inpatient nurse clinical documentation
- Radiology reports
- Operative reports
- Procedural notes
- Discharge summary
- Death note and certificate

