### **22.2 Data Safety and Monitoring Board**

ROC has an existing independent Data Safety and Monitoring Board (DSMB) that will monitor adverse events throughout the trial and review outcomes data for possible harm. The DSMB was appointed by NHLBI. The committee will review and approve the protocol before the study commences. In addition, the committee will approve an interim monitoring plan before study initiation and review the results of the interim analyses. Although the DSMB will make the final decision about the interim monitoring plan, we anticipate that the DSMB will evaluate treatment compliance and the rate of adverse events between the treatment and control arms at intervals to be determined by the DSMB, expected to be approximately semi-annually. The DSMB will also monitor primary, secondary and mechanistic study outcomes between the treatment and control groups including main effects and a priori subgroups as specified elsewhere in the protocol. The DSMB will advise the investigators if a change in the protocol is warranted based on this interim monitoring.

The DCC will forward DSMB reports to study investigators, the Institutional Review Board, and the sponsor in accordance with the 1996 guidance from OHRP regulations 46.101 (i), as is our current practice.

Clinical staff will report all potential adverse events to the coordinating center as soon as possible. These will be collected in both a structured (standard form) and open (describing any difficulties encountered) form. All potential adverse events will be reviewed as to treatment arm and further classified by: a) Severity (life-threatening, serious, non-serious); and b) Expected vs. Unexpected. Expected adverse events will be recorded as noted in the hospital discharge summary by each enrolling site, reported to overseeing agencies as required by federal regulations and local requirements, and reviewed periodically by our independent data safety monitoring board.

For suspected unexpected serious adverse reactions (SUSAR), the coordinating center will promptly notify the DSMB as well as appropriate regulatory agencies, site and sponsor. The coordinating

center will tabulate and report compliance, data quality, and non-serious adverse events on a regular basis.

The SMC will carry out recommendations provided by the DSMB.

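### Airway swelling is determined from EMS and ED records, although its surveillance window can run to 24 hours of hospitalization and section 22.2 names a different source

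*Combined protocol and SAP*

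**What the plan says.** The entry on airway swelling or edema in section 14.3.2 makes four statements that matter here.

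- **Source.** The event "will be based upon EMS and ED personnel assessment and will be determined from EMS and ED patient care records".
- **Usual timing.** It is "usually associated with instances of prolonged LT ventilation (several hours"), with the qualification that "some clinicians have reported the occurrence of this event during resuscitative efforts".
- **Window.** Surveillance is "limited to the earlier of a) replacement of the LT with an ET tube, or b) the first 24 hours of hospitalization".
- **Scope.** It is monitored whichever airway device was inserted.

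Section 22.2 gives a general source rule: "Expected adverse events will be recorded as noted in the hospital discharge summary by each enrolling site". Section 19.1 plans a review of all EMS and hospital records. Section 19.1.2 lists the hospital records that may be reviewed, among them "Emergency Department and inpatient physician clinical documentation", nursing documentation, procedural notes and the discharge summary, without assigning any of them to this event.

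**The concern.** A window and its data source should cover the same period. Here the window can extend beyond the ED stay, but the assessors and records named for the event are confined to EMS and the ED. The uncovered stretch includes the time at which, by the protocol's own account, swelling usually appears.

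Section 15.4 includes adverse events in the comparison of the arms, and section 22.2 expects the DSMB to review adverse event rates by arm. Section 14.3.2 introduces swelling as a recognised LT complication that can interfere with ventilation. If sites follow 14.3.2 literally, swelling first seen in the ICU or on the ward is not counted. If they follow 22.2, it is counted when the discharge summary mentions it. Sites could differ, and a low count could not be told apart from incomplete recording.

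**Working it through.** The plan states no figure for this event, so there is none to reproduce. The check is a comparison of passages, followed by an illustration.

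**1. Source against window, by type of patient (14.3.2 as worded)**

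| Patient | Window ends | In-window time after the ED | Source named in 14.3.2 for that time |
|---|---|---|---|
| LT replaced by an ET tube in the ED | at replacement | none | not needed |
| Leaves the ED with the LT in place | at replacement or 24 h, whichever is earlier | yes | none |
| No LT, admitted | 24 h (the replacement clause cannot apply) | yes | none |
| Dies before leaving the ED | at death | none | not needed |

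The gap concerns the second and third rows, and the third row occurs mainly outside LT use.

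**2. Comparison with neighbouring entries in 14.3.2**

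- Oropharyngeal or hypopharyngeal injury: first 24 hours; discharge summary and ED physician records.
- Pneumonia and aspiration pneumonitis: first 72 hours; radiology interpretation of imaging from that period.
- Pneumothorax: first chest imaging in the ED; radiology or ED physician reading.
- Airway swelling: up to 24 hours; EMS and ED records.

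Among these, only swelling has a window that can outlast its named sources.

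**3. Section 14.3.2 against section 22.2**

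Swelling is on the list of expected adverse events, so the discharge-summary sentence in 22.2 applies to it as well. Nothing says which section governs.

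**4. Illustration of under-counting (assumed rates)**

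Inputs: 1,306 per arm (section 16.1) and two-sided 0.05. The standard error is multiplied by 1.05, which is one reading of the 5% loss of precision in 16.1. The true rates (2.0% LT, 0.75% ETI) and the capture fraction c are assumptions, with no source in the documents.

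Reported rates are c × 2.0% and c × 0.75%. SE = 1.05 × √{[p₁(1−p₁) + p₂(1−p₂)]/1,306}. Power = Φ(difference/SE − 1.96).

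At c = 1: expected events 1,306 × 0.02 = 26 and 1,306 × 0.0075 = 10; SE = 0.00478; power = Φ(0.0125/0.00478 − 1.96) = 0.74.

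| c in both arms | Reported difference (points) | Power |
|---|---|---|
| 1.00 | 1.25 | 0.74 |
| 0.75 | 0.94 | 0.62 |
| 0.50 | 0.63 | 0.45 |
| 0.25 | 0.31 | 0.25 |

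Other assumed rates, without the 1.05 factor and with a pooled variance under the null, for c = 1 and then c = 0.5: 1.5% vs 0.5%, power 0.73 and 0.44; 2.0% vs 0.5%, 0.93 and 0.68; 3.0% vs 1.0%, 0.955 and 0.73.

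**5. Direction**

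With the 2.0% and 0.75% rates and unequal capture:

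- LT 50%, ETI 90%: 0.02 × 0.5 − 0.0075 × 0.9 = 1.00% − 0.675% = 0.325 points, below the true 1.25.
- LT 90%, ETI 50%: 0.02 × 0.9 − 0.0075 × 0.5 = 1.80% − 0.375% = 1.425 points, above the true 1.25.

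The sign of the error depends on which arm loses more events, and the documents do not settle that.

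**The case against.** A reader might infer that late swelling is captured from EMS and ED records alone and is simply lost. The documents do not support that. Section 22.2 adds the discharge summary, section 19.1 plans review of all hospital records, and 19.1.2 lists inpatient notes. This objection stands against the stronger reading. It does not remove the conflict: the event-specific rule still differs from the general one, 19.1.2 only says what may be reviewed, and a discharge summary may leave out transient swelling or not show whether it arose inside the window.

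A reader might also infer that the loss falls mainly on the LT arm and makes LT look safer. That is not established either. The ED guidance in section 21 encourages keeping the LT during resuscitation and converting after ROSC, so for patients converted in the ED the window has already closed and the source rule loses nothing. Patients without an LT have no replacement stop and may have the longer post-ED window. Against this, section 12.5.6 says ED practice varies and is not dictated, so some patients may be admitted with the LT in place.

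Three further objections have some force. Swelling is also reported during resuscitation, which EMS and ED records can capture. The trial's pragmatic scope is out-of-hospital airway care. No power is claimed for this event, since the sample size rests on 72-hour survival. These limit the importance of the point, but they do not explain setting a window of up to 24 hours and naming sources that need not cover it.

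**Conclusion.** The mismatch is real and follows from the text alone: the sources in 14.3.2 do not cover the window in 14.3.2, and they differ from the source in 22.2. Swelling first noted after ED departure and inside the window has no named source under 14.3.2. The affected patients are those admitted with the LT still in place and admitted patients without an LT.

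The consequence is possible under-counting of a safety outcome and possible inconsistency between sites. Its size is unknown, because it depends on the swelling rate, the time spent in the ED and the number of patients in those two groups, none of which the documents give. Its direction between arms is also unknown. The power figures show only that incomplete capture of a rare event matters under assumed rates; they do not estimate what this trial would lose. Swelling after an ET tube replaces the LT is excluded by the window itself, not by the source rule, and is not part of this point.

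**What to change.** Reconcile the source sentence in 14.3.2 with its own window and with 22.2. Suggested wording for 14.3.2: *In both arms, this event will be determined from EMS, ED and inpatient physician, nursing and procedural records and from the discharge summary, for the whole of the surveillance window stated in this section.* Add a form field recording whether swelling was first noted by EMS, in the ED or as an inpatient. In 22.2, refer to the event-specific sources in 14.3.2.

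The sentence should refer to the stated window and not to a flat 24 hours, because the sentence that follows ends surveillance at LT replacement and the two must agree.

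The cost is a wording change in two sections, one form field and some extra chart abstraction for admitted patients. The records are already listed in 19.1.2, although the existing 24-hour check for oropharyngeal injury uses only the discharge summary and ED physician records, so inpatient nursing and procedural notes would be additional work. Some swelling from other causes will be picked up, but it would be recorded in both arms. Clinical care is unchanged.

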### Outcomes:

The primary outcome will be:

- 1) **72-hour hospital survival**, defined as patient status (alive/dead) at 72 hours after the initial onset of cardiac arrest.

Secondary outcomes will include:

- 1) **Return of Spontaneous Circulation (ROSC)**, defined as the presence of palpable pulses upon ED arrival.
- 2) **Airway Management Clinical Course**, including sequence of ETI/LT insertion, ETI/LT insertion success and time, number of ETI/LT insertion attempts, and airway conversion (change of LT-to-ETI, or ETI-to-LT) in the receiving Emergency Department.
- 3) **Adverse Events**, including initially unrecognized airway misplacement (including endotracheal tube misplacement), inadequate ventilation requiring airway exchange, vomiting, oropharyngeal, hypopharyngeal or gastrointestinal trauma, and pneumothorax.
- 4) **Hospital Survival**, defined as patient status (alive/dead) at hospital discharge.

- 5) **Hospital Survival with Good Neurologic Function**, defined as Modified Rankin Score  $\leq 3$  upon hospital discharge.

**Analysis:** We will calculate the difference in outcomes divided by the estimated “robust” standard error based on the Huber-White sandwich estimator in order to account for within cluster correlation and variability, which might depart from the classical assumptions. To quantify the treatment effect, we will calculate the 95% CI for the difference in event rates. We will perform the analysis on an intention-to-treat (primary analysis) as well as treatment-received bases (secondary analysis).

**Sample Size:** The trial will require 2,612 subjects (1,306 per group) to have 85% power to detect a 4.5% absolute difference in 72-hour survival, given baseline survival of 13.7% and an overall two-sided alpha of 0.05. To allow for subject withdrawal and lost-to-follow-up, the trial will enroll up to 3,000 subjects.

**Regulatory and Ethical Considerations:** The trial will be carried out under federal rules for Exception from Informed Consent (EFIC) outlined by the guidance document “Waiver of Informed Consent Requirements in Certain Emergency Research” (Federal Register, Vol. 61, pp. 51531-51533, November 1, 1996 - <http://www.gpo.gov/fdsys/pkg/FR-1996-10-02/html/96-24968.htm>), OHRP “Basic HHS Policy for Protection of Human Research Subjects” (45 CFR 46.101(i) - <http://www.hhs.gov/ohrp/humansubjects/guidance/45cfr46.html#46.101>), and FDA regulations 21 CFR 50.24.

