### **12.5.3 Confirmation of Airway Placement**

An important adverse event of ETI is initially unrecognized misplacement of the ET tube, including unrecognized placement in the esophagus or hypopharynx. Unrecognized misplacement of the ET tube may result in suboptimal delivery of oxygen to the lungs. National consensus guidelines recommend the use of multiple techniques for confirming proper ET tube placement, including auscultation of lungs (for presence of breath sounds) and epigastrium (for absence of gastric sounds), use of an esophageal detector device (bulb detector device), use of a colorimetric end-tidal carbon dioxide detector, or use of a digital or waveform end-tidal carbon dioxide detector. ET tube misplacement may impact the apparent effectiveness of the ETI arm. Therefore, this trial will monitor the techniques used for verifying ET tube placement.

While this trial will not dictate ET tube placement confirmation techniques, best practices for verifying tube placement will be emphasized during training. We will similarly encourage receiving EDs to use best practices when verifying the proper placement of an EMS placed ET tube.

Airway misplacement is less of a concern for the LT because the device is intended to be placed in the esophagus. Because of the design of the LT, it is highly unusual for the device to be placed intratracheally. There are no national guidelines for verifying proper LT placement.

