### 14.3.2 Expected Adverse Events

The following are events commonly observed in patients who experience cardiac arrest or resuscitative efforts after its onset, or who receive airway management efforts, and may or may not be attributable to specific resuscitation therapies. These events will be monitored and reported but not considered as adverse events of the study intervention.

- **Unsuccessful EMS airway insertion.** This event includes unsuccessful EMS ETI or LT insertion efforts. This event does not include ED airway insertion efforts. This event will be determined from EMS records.
- **Multiple EMS airway insertion attempts.** This event includes 3 or more EMS attempts to perform ETI, or 3 or more EMS attempts to insert the LT. This event does not include ED airway management efforts. This event will be determined from EMS records.
- **Unrecognized EMS airway misplacement or dislodgement.** This event includes unrecognized EMS endotracheal tube placement in the esophagus or hypopharynx, or displacement of a correctly placed ET tube. Airway misplacement and dislodgements are difficult to differentiate; this trial will not differentiate these events. Airway misplacement/dislodgement events will be determined from EMS and ED records.

This event does not include right mainstem intubations. This event does not include instances where EMS personnel immediately recognize and correct ET tube misplacement. This event does not include ED airway misplacements.

Misplacement and dislodgement events are unique to ETI and do not apply to the LT.

- **Inadequate EMS ventilation.** This event includes instances where EMS personnel a) perceive that a successfully inserted airway device is resulting in inadequate ventilation and b) therefore opt to change to another airway management device or technique. Inadequate ventilation connotes a) inability to insufflate any oxygen (airway obstruction) or b) inadequate chest rise on insufflation. Potential reasons for inadequate ventilation may include device obstruction, misplacement, malfunction or cuff leak, among others.

Inadequate ventilation will be based upon EMS personnel assessment, and will be determined from EMS patient care records.

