## 21. Guidance for Receiving Emergency Departments

The practices and procedures employed by receiving Emergency Departments will not be dictated by this trial. However, to each potential receiving ED we will provide information on best ED practices for managing EMS-placed airways. This information will include:

- **Overview of the Trial** – We will provide an overview of the rationale for the trial and the trial interventions. We will provide an overview of the LT airway and its function.
- **Best Practices for Confirming EMS ET Tube Placement** – Best practices for confirming EMS ET tube placement will be reviewed. Emphasis will be placed on a) the need for using multiple modalities for confirming ET tube placement, b) the use of waveform capnography as a preferred modality for confirming tube placement, c) the use of direct laryngoscopic revisualization when placement is uncertain. Emphasis will be placed on the preference of maintaining EMS ET tube use over emergent ED re-intubation.
- **Best Practices and Strategies for Managing EMS-Inserted LT Airways** – Best practices for confirming EMS LT airway placement will be reviewed. The guidelines will encourage

using of the EMS LT for ongoing resuscitation, with conversion to ETI deferred until ROSC. Strategies for LT conversion to ETI will be reviewed, including direct laryngoscopy and intubation, exchange of LT to ET tube over a bougie, exchange of LT to ET tube over an Aintree catheter, and cricothyroidotomy or tracheotomy.

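### Airway swelling and unrecognized misplacement (14.3.2) are ascertained unequally by device, although adverse events are compared between assigned arms

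*Combined protocol and SAP*

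**What the plan says.** **Swelling (14.3.2).** The item states: "The timeframe for surveillance for this event will be limited to the earlier of a) replacement of the LT with an ET tube"; the other limit is the first 24 hours of hospitalization. The item is not confined to LT patients: "we will monitor the occurrence of airway swelling or edema regardless of inserted airway device". On sources, it "will be based upon EMS and ED personnel assessment and will be determined from EMS and ED patient care records". Section 21 tells receiving EDs that the guidelines will encourage "using of the EMS LT for ongoing resuscitation, with conversion to ETI deferred until ROSC".

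**Misplacement or dislodgement (14.3.2).** The event covers unrecognized ET tube placement in the esophagus or hypopharynx and displacement of a correctly placed ET tube, taken from EMS and ED records. The item closes: "Misplacement and dislodgement events are unique to ETI and do not apply to the LT". Section 12.5.3 gives the reason: the LT is meant to sit in the esophagus, and "it is highly unusual for the device to be placed intratracheally". The Summary (section 3, Outcomes) is worded more widely. It lists adverse events "including initially unrecognized airway misplacement (including endotracheal tube misplacement", so the ET tube appears as one case of a broader term.

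**Use of these events.** The Summary lists adverse events as a secondary outcome. Section 15.4 analyses them in the same way as the primary outcome, and sections 12.5.2 and 15.2 make assigned arm the intention-to-treat basis. Under 22.2 the DSMB looks at adverse event rates by arm, and 16.2 names safety outcomes by treatment group among the factors that may influence stopping.

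**The concern.** A between-arm comparison of event counts is interpretable only if an event of a given kind has the same chance of being recorded in each arm. Here two of the eight expected events do not meet that condition.

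For swelling, observation time depends on a post-randomization step that only LT patients can undergo. The cut-off may also be informative. Section 14.3.2 says swelling can interfere with ventilation, and 12.5.6 says a malfunctioning LT may be replaced at once. Swelling that prompts an exchange can therefore end its own surveillance. The text does not say whether swelling seen at the exchange counts.

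For misplacement, an LT cannot score whatever its position.

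At stake is the reading of the safety comparison by the DSMB and in the final report. A lower LT count for either event could reflect the counting rule rather than the device.

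**Working it through.** The plan states no figure for either event, so there is nothing to reproduce. The check is of the definitions, followed by an illustration of size under stated assumptions.

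**1. Swelling: the windows side by side**

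- ET tube only: the replacement limit cannot occur, so the nominal window is 24 hours of hospitalization.
- LT, never exchanged: 24 hours, the same.
- LT, exchanged at time *t*: the window ends at *t*.

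Ending surveillance early can remove events but cannot add them, so the direction is fixed. The size depends on the fraction exchanged (*f*), the exchange time (*t*) and when swelling arises. The documents give none of these.

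Illustration. Assume the same true 24-hour risk *p* in both arms, a constant hazard, every ETI patient watched for 24 hours, and no rescue devices. Then

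- hazard: *h* = −ln(1 − *p*)/24
- observed LT risk: *f*·(1 − exp(−*h·t*)) + (1 − *f*)·*p*
- ratio: observed LT risk / *p*

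With *p* = 0.01, *f* = 0.5 and *t* = 1 hour: *h* = 0.01005/24 = 0.000419 per hour. The exchanged half contributes 0.5 × 0.000419 = 0.0002 and the rest 0.5 × 0.01 = 0.005. The sum is 0.0052, and the ratio is 0.52.

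| Fraction exchanged (assumed) | Exchange time (assumed) | Ratio, *p* = 1% | Ratio, *p* = 5% |
|---|---|---|---|
| 50% | 1 h | 0.52 | 0.52 |
| 80% | 1 h | 0.23 | 0.23 |
| 80% | 4 h | 0.33 | 0.34 |
| 50% | 12 h | 0.75 | 0.75 |

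The true ratio is 1 in every row. The distortion would be smaller if swelling arises mainly while the LT is in place, or if reliance on EMS and ED records ends ETI surveillance well before 24 hours.

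**2. Misplacement: where each event is counted**

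| Situation | ET tube | LT |
|---|---|---|
| EMS perceives inadequate ventilation and changes device | Inadequate ventilation item | Inadequate ventilation item (misplacement is a listed cause) |
| EMS does not recognize it; found in the ED | Misplacement item, from EMS and ED records | No structured item |

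The ED airway-course variable (14.2.2) would show that an EMS-placed LT was replaced, but its listed categories carry no reason.

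Illustration. Take the planned 1,306 per arm (16.1) and suppose no countable event in the LT arm. An assumed ETI rate of 0.5% gives 0.005 × 1,306 = 6.5, say 7 events; Fisher's exact test of 7/1,306 against 0/1,306 gives p = 0.0155. A rate of 1% gives 13 events and p = 0.0002. The test ignores clustering. It shows only that a nominally significant difference could come from the definition if unrecognized LT malposition were in truth as common. Whether it is, the documents do not say.

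**The case against.** The best defence is that the definitions follow the devices. An LT is designed for the esophagus, so esophageal placement is not an error for it, and 12.5.3 says so openly. An on-device window for swelling is also defensible: once the LT is out, an ET tube and ED laryngoscopy are competing causes. Section 14.3.2 states that expected events are monitored and reported but not treated as adverse events of the intervention. Section 22.2 provides open reporting of any potential adverse event, reviewed by arm, so a serious LT malposition need not go unseen.

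Much of this stands. It explains the rules and limits their effect, but it does not make the counts comparable. Esophageal position is only one form of malposition, and the inadequate-ventilation item itself names misplacement as a cause without restriction by device. The trial compares strategies, so swelling noticed at or after an exchange belongs to the assigned strategy. Open reporting is not a structured count with equal ascertainment. Whatever the events are called, 15.4 compares them between arms.

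A reader might go further and infer that the safety comparison was designed to favour the LT. The documents do not support that: a device-based reason is given, no intent appears, and the other six expected events (unsuccessful insertion, multiple attempts, inadequate ventilation, oropharyngeal or hypopharyngeal injury, pneumothorax, pneumonia or aspiration pneumonitis) apply one rule to both devices.

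A reader might also infer that LT patients get only a small fraction of the ETI window, or that the LT arm must show zero misplacements. Neither follows. Deferral until ROSC is advice with no clock time, ED practice varies (12.5.6), and patients who never regain pulses may never be exchanged. The rules attach to the device, not the arm. A rescue ET tube in the LT arm can score misplacement, and a rescue LT in the ETI arm can meet the replacement limit.

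**Conclusion.** The concern holds for these two events. As written, swelling is watched for less time in patients whose LT is exchanged, and an unrecognized malposition or dislodgement has a structured count for an ET tube but not for an LT. Both tend to lower the count attributed to the LT in a comparison made by assigned arm.

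The size cannot be derived from the documents. The ratios of 0.23 to 0.75 and the Fisher p-values rest on assumed exchange patterns and event rates, and show only that the effect need not be trivial. Rescue devices soften the contrast, and the limits of EMS and ED records may narrow the swelling gap.

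The primary outcome, 72-hour survival, is untouched. This should be corrected because the safety comparison depends on it and the correction is cheap; it does not call the trial's main result into question.

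**What to change.** 1. **Swelling.** Use one window for every patient regardless of exchange, for example the first 24 hours of hospitalization, which 14.3.2 already uses for oropharyngeal or hypopharyngeal injury. State that swelling noted at or after exchange counts, and use the same record sources in both arms. If the window is to reach 24 hours in practice, add inpatient notes, which 19.1.2 already lists as reviewable.
2. **Misplacement wording.** Reconcile the Summary with 14.3.2 on whether the event covers ET tubes alone or any airway.
3. **Misplacement analysis.** Report ET tube misplacement descriptively, not as a between-arm test. For the arm comparison, add a device-neutral item: unrecognized malposition, dislodgement or non-ventilating position of any EMS-placed advanced airway, from EMS and ED records in both arms.

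The cost is a revised case-form definition, an instruction to abstractors and some extra abstraction. There are two drawbacks. A fixed window will take in some swelling related to ED intubation; recording whether onset was before, at or after exchange would let readers see how much. And since 12.5.3 notes that no national guideline exists for verifying LT placement, the new item needs a short operational definition so that it is judged alike for both devices.
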